Rash not at injection site																
Nonpurulent conjunctivitis																
Headache																
Respiratory distress																
Retro-orbital pain																
Myalgia/Muscle pain																
Arthralgia/Joint pain																
Arthritis																
Nausea																
Abdominal pain																
Vomiting*																
Persistent vomiting*																
Bleeding*																

Table 175: Duration (Days) of Symptoms of AFI/ARI Events Reported Through 12 Months Post Final Vaccination by Treatment Group – All Subjects (continued)

Symptom	2.5 mcg ZPIV (N=X)	5 mcg ZPIV (N=X)	Placebo (N=X)	All Subjects (N=X)
N = number of subjects reporting at least one AFI/ARI				
n = number of subjects reporting the symptom				
If multiple AFI/ARI are reported for a subject, then the maximum severity is considered for each symptom; if multiple AFI/ARI are reported for a subject, then the maximum duration is considered for each symptom				
This table includes subjects who only received dose 1.				
* Reported as None/Any				

Tables with similar format:

Table 176: Duration (Days) of Symptoms of AFI/ARI Events Reported Through 12 Months Post Final Vaccination by Treatment Group – Baseline ZIKV Seropositive Subjects

Table 177: Duration (Days) of Symptoms of AFI/ARI Events Reported Through 12 Months Post Final Vaccination by Treatment Group – Baseline ZIKV Seronegative Subjects

Table 178: Duration (Days) of Symptoms of AFI/ARI Events Reported Through 12 Months Post Final Vaccination by Treatment Group – Baseline ZIKV Seropositive and DENV Seropositive Subjects

Table 179: Duration (Days) of Symptoms of AFI/ARI Events Reported Through 12 Months Post Final Vaccination by Treatment Group – Baseline ZIKV Seropositive and DENV Seronegative Subjects

Table 180: Duration (Days) of Symptoms of AFI/ARI Events Reported Through 12 Months Post Final Vaccination by Treatment Group – Baseline ZIKV Seronegative and DENV Seropositive Subjects

Table 181: Duration (Days) of Symptoms of AFI/ARI Events Reported Through 12 Months Post Final Vaccination by Treatment Group – Baseline ZIKV Seronegative and DENV Seronegative Subjects

Table 182: Duration (Days) of Symptoms of AFI/ARI Events Reported Through 12 Months Post Final Vaccination by Treatment Group and ZIKV or DENV Infection Confirmation Status – All Subjects

[Implementation note: This table can include any subjects who did not have a baseline flavivirus status observed.]

Symptom	Infection Confirmation Status	2.5 mcg ZPIV (N*=X)				5 mcg ZPIV (N*=X)				Placebo (N*=X)				All Subjects (N*=X)			
		n	Mean (SD)	Median	Min, Max	n	Mean (SD)	Median	Min, Max	n	Mean (SD)	Median	Min, Max	n	Mean (SD)	Median	Min, Max
Any Symptom	Positive by PCR ^a	x	x.x (x.x)	x.x	x, x	x	x.x (x.x)	x.x	x, x	x	x.x (x.x)	x.x	x, x	x	x.x (x.x)	x.x	x, x
	Positive by 4-Fold Titer Rise ^b																
	Any Positive Confirmation ^{a,b}																
	Negative Lab Confirmation																
Fever																	
Feverishness																	
Lethargy																	
Restlessness																	
Rash not at injection site																	
Nonpurulent conjunctivitis																	
Headache																	
Respiratory distress																	
Retro-orbital pain																	
Myalgia/Muscle pain																	
Arthralgia/Joint pain																	
Arthritis																	

Table 182: Duration (Days) of Symptoms of AFI/ARI Events Reported Through 12 Months Post Final Vaccination by Treatment Group and ZIKV or DENV Infection Confirmation Status – All Subjects (continued)

Symptom	Infection Confirmation Status	2.5 mcg ZPIV (N*=X)				5 mcg ZPIV (N*=X)				Placebo (N*=X)				All Subjects (N*=X)			
		n	Mean (SD)	Median	Min, Max	n	Mean (SD)	Median	Min, Max	n	Mean (SD)	Median	Min, Max	n	Mean (SD)	Median	Min, Max
Nausea																	
Abdominal pain																	
Vomiting*																	
Persistent vomiting*																	
Bleeding*																	

N* = number of subjects reporting at least one AFI/ARI

n = number of subjects reporting the symptom

If multiple AFI/ARI are reported for a subject, then the maximum severity is considered for each symptom; if multiple AFI/ARI are reported for a subject, then the maximum duration is considered for each symptom.

This table includes subjects who only received dose 1.

a PCR confirmation includes a positive PCR result for at least one of ZIKV (blood or urine) or DENV.

b 4-fold rise in either ZIKV or DENV neutralization titers after the ARI/AFI illness visit compared to before the illness visit.

* Reported as None/Any

Table with similar format:

Table 183: Duration (Days) of Symptoms of AFI/ARI Events Reported Through 12 Months Post Final Vaccination by Treatment Group and ZIKV or DENV Infection Confirmation Status – Baseline ZIKV Seropositive Subjects

Table 184: Duration (Days) of Symptoms of AFI/ARI Events Reported Through 12 Months Post Final Vaccination by Treatment Group and ZIKV or DENV Infection Confirmation Status – Baseline ZIKV Seronegative Subjects

Table 185: Duration (Days) of Symptoms of AFI/ARI Events Reported Through 12 Months Post Final Vaccination by Treatment Group and ZIKV or DENV Infection Confirmation Status – Baseline ZIKV Seropositive and DENV Seropositive Subjects

Table 186: Duration (Days) of Symptoms of AFI/ARI Events Reported Through 12 Months Post Final Vaccination by Treatment Group and ZIKV or DENV Infection Confirmation Status – Baseline ZIKV Seropositive and DENV Seronegative Subjects

Table 187: Duration (Days) of Symptoms of AFI/ARI Events Reported Through 12 Months Post Final Vaccination by Treatment Group and ZIKV or DENV Infection Confirmation Status – Baseline ZIKV Seronegative and DENV Seropositive Subjects

Table 188: Duration (Days) of Symptoms of AFI/ARI Events Reported Through 12 Months Post Final Vaccination by Treatment Group and ZIKV or DENV Infection Confirmation Status – Baseline ZIKV Seronegative and DENV Seronegative Subjects

14.3.2 Listing of Deaths, Other Serious and Significant Adverse Events**Table 189: Listing of Serious Adverse Events**

Adverse Event	Associated with Dose No.	No. of Days Post Associated Dose (Duration)	No. of Days Post Dose the Event Became Serious	Reason Reported as an SAE	Severity	Relationship to Study Treatment	If Not Related, Alternative Etiology	Action Taken with Study Treatment	Subject Discontinued Due to AE	Outcome	MedDRA System Organ Class	MedDRA Preferred Term
Subject ID: , Treatment Group: , Baseline Flavivirus Immune Status:, AE Number:												
Comments:												
Subject ID: , Treatment Group: , Baseline Flavivirus Immune Status:, AE Number:												
Comments:												
Listing includes serious adverse events reported at any time during the study.												

Table 190: Listing of Non-Serious, Unsolicited, Moderate or Severe Adverse Events

Adverse Event	Associated with Dose No.	No. of Days Post Associated Dose (Duration)	Severity	Relationship to Study Treatment	If Not Related, Alternative Etiology	Action Taken with Study Treatment	Subject Discontinued Due to AE	Outcome	MedDRA System Organ Class	MedDRA Preferred Term
Subject ID: , Treatment Group: , Baseline Flavivirus Immune Status:, AE Number:										
Comments:										
Subject ID: , Treatment Group: , Baseline Flavivirus Immune Status:, AE Number:										
Comments:										

Table 191: Listing of AESIs and NOCMCs

[Implementation Note: sort order is Subject ID, Number of Doses Received at Time of Event, and Date of Product Administration.]

Adverse Event	Number of Doses Received at Time of Event	No. of Days Post Associated Dose	Duration of Event	Severity	MedDRA System Organ Class	AESI?	NOCMC?	Relationship	Outcome
Subject ID: , Treatment Group: , Baseline Flavivirus Immune Status:, AE Number:									
Comments:									
Subject ID: , Treatment Group: , Baseline Flavivirus Immune Status:, AE Number:									
Comments:									

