6.5. Missing Data

No imputation will be performed for missing values. Missing data are assumed to be missing completely at random.

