9.3. Adverse Events

When calculating the incidence of adverse events (i.e., on a per subject basis), each subject will only be counted once per AE using the event with maximum severity and any repetitions of adverse events within a subject will be ignored; the denominator will be the total treatment group size or the corresponding number of subjects receiving the second dose, as appropriate. All unsolicited adverse events reported will be included in [Listing 11](#).

An overall summary of adverse events from first administration of study vaccine to the end of the study is presented in [Table 36](#), [Table 37](#), and [Table 38](#) for all subjects, baseline flavivirus positive subjects and baseline flavivirus negative subjects, respectively.

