9.3.1. Solicited Events and Symptoms

Statistical comparisons of the frequency and duration of vaccine related Grade 3 local, systemic, or laboratory AE, and Grade 2 or greater local or systemic reactogenicity are presented post dose 1, post dose 2, and post any dose in [Table 43](#), overall and by pre-vaccination flavivirus immune status. Frequencies of each adverse event are compared between dosage groups using Fisher’s Exact test. The distribution of the duration of adverse events (excluding laboratory AEs) will be compared between all dosage groups using the 2-samples Wilcoxon rank sum test.

The frequency and proportion of subjects experiencing any local or systemic solicited event over the 8-day post-vaccination reporting period will be summarized by dose number, pre-vaccination flavivirus immune status, severity and treatment group in [Table 44](#) (post dose 1, post dose 2, and post any dose).

The number, percentage, and exact 95% CI of subjects experiencing each solicited event over the 8-day post-vaccination reporting period, collected in-clinic pre-vaccination, post-vaccination and via memory aid, will be summarized by pre-vaccination flavivirus immune status, dose number and symptom in [Table 45](#) (all subjects), [Table 46](#) (baseline ZIKV seropositive subjects), [Table 47](#) (baseline ZIKV seronegative subjects), [Table 48](#) (baseline ZIKV seropositive and DENV seropositive subjects), [Table 49](#) (baseline ZIKV seropositive and DENV seronegative subjects), [Table 50](#) (baseline ZIKV seronegative and DENV seropositive subjects), and [Table 51](#) (baseline ZIKV seronegative and DENV seronegative subjects).

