Symptom		2.5 mcg ZPIV (N=X)	5 mcg ZPIV (N=X)	Placebo (N=X)	All Subjects (N=X)
Post Dose 1					
Any Local Reaction	n (%)	x (xx)	x (xx)	x (xx)	x (xx)
	95% CI	xx.x, xx.x	xx.x, xx.x	xx.x, xx.x	xx.x, xx.x
Repeat for:					
Pain					
Erythema					
Induration (mm)					
Induration					
Pruritis					
Ecchymosis					
Tenderness					
Any Systemic Reaction	n (%)	x (xx)	x (xx)	x (xx)	x (xx)
	95% CI	xx.x, xx.x	xx.x, xx.x	xx.x, xx.x	xx.x, xx.x
Repeat for:					
Feverishness					
Fatigue					
Malaise					
Myalgia					
Arthralgia					
Headache					
Nausea					
Vomiting					
Diarrhea					
Abdominal Pain					
Rash					
Fever					
Repeat for:					
Post Dose 2					
Post Any Dose					
Each event is defined as any grade 1, 2 or 3 solicited reaction within 7 days following either dose.					
N = Number of subjects in the safety population who received the specified dose; used as the denominator for percentages.					
n = Number of subjects reporting an event					

Tables with similar format:

Table 46: Number, Percentage and 95% Confidence Interval of Subjects Experiencing Any Grade 1 or Greater Solicited Adverse Event, by Dose, Symptom and Treatment Group – Baseline ZIKV Seropositive Subjects

[Implementation note: N = Number of subjects in the Safety population with the specified flavivirus immune status at baseline.]

Table 47: Number, Percentage and 95% Confidence Interval of Subjects Experiencing Any Grade 1 or Greater Solicited Adverse Event, by Dose, Symptom and Treatment Group – Baseline ZIKV Seronegative Subjects

[Implementation note: N = Number of subjects in the Safety population with the specified flavivirus immune status at baseline.]

Table 48: Number, Percentage and 95% Confidence Interval of Subjects Experiencing Any Grade 1 or Greater Solicited Adverse Event, by Dose, Symptom and Treatment Group – Baseline ZIKV Seropositive and DENV Seropositive Subjects

[Implementation note: N = Number of subjects in the Safety population with the specified flavivirus immune status at baseline.]

Table 49: Number, Percentage and 95% Confidence Interval of Subjects Experiencing Any Grade 1 or Greater Solicited Adverse Event, by Dose, Symptom and Treatment Group – Baseline ZIKV Seropositive and DENV Seronegative

[Implementation note: N = Number of subjects in the Safety population with the specified flavivirus immune status at baseline.]

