Table 50: Number, Percentage and 95% Confidence Interval of Subjects Experiencing Any Grade 1 or Greater Solicited Adverse Event, by Dose, Symptom and Treatment Group – Baseline ZIKV Seronegative and DENV Seropositive

[Implementation note: N = Number of subjects in the Safety population with the specified flavivirus immune status at baseline.]

Table 51: Number, Percentage and 95% Confidence Interval of Subjects Experiencing Any Grade 1 or Greater Solicited Adverse Event, by Dose, Symptom and Treatment Group – Baseline ZIKV Seronegative and DENV Seronegative

[Implementation note: N = Number of subjects in the Safety population with the specified flavivirus immune status at baseline.]

Table 52: Number and Percentage of Subjects Experiencing Solicited Local Events by Dose, Reaction, Severity and Treatment Group – All Subjects

Local Reactions, Post Dose 1							
All Subjects							
		2.5 mcg ZPIV (N=X)		5 mcg ZPIV (N=X)		Placebo (N=X)	
Reaction	Severity	n	%	n	%	n	%
Any Local Reaction	None	x	xx	x	xx	x	xx
	Mild						
	Moderate						
	Severe						
	Not Reported						
Repeat for:							
Pain							
Erythema							
Induration (mm)							
Induration							
Pruritis							
Ecchymosis							
Tenderness							
Repeat for:							
Local Reactions, Post Dose 2							
All Subjects							
Local Reactions, Post Any Dose							
All Subjects							
Subjects who reported not having a symptom are listed as “None”, while subjects who did not complete their Memory Aid or could not remember whether they had a symptom are listed as “Not Reported”.							
Severity is the maximum severity reported over all solicited symptoms post dosing for each subject.							
N=Number of subjects in the Safety Population who received the specified dose.							
n = Number of subjects reporting an event							
For subjects receiving vaccinations in both arms, the maximum severity in either arm is summarized							

Tables with similar format:

Table 53: Number and Percentage of Subjects Experiencing Solicited Local Events by Dose, Reaction, Severity, and Treatment Group – Baseline ZIKV Seropositive Subjects

[Implementation note: N = Number of subjects in the Safety population with the specified flavivirus immune status at baseline.]

Table 54: Number and Percentage of Subjects Experiencing Solicited Local Events by Dose, Reaction, Severity, and Treatment Group – Baseline ZIKV Seronegative Subjects

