Mild																				
Moderate																				
Severe																				
Not Reported																				
Repeat for:																				
Solicited Local Events																				
Any Local Reaction																				
Pain																				
Erythema																				
Induration (mm)																				
Induration																				
Pruritis																				
Ecchymosis																				
Tenderness																				
Solicited Systemic Events																				
Any Systemic Reaction																				
Feverishness																				
Fatigue																				
Malaise																				

Table 66: Number and Percentage of Subjects Experiencing Solicited Local or Systemic Events by Symptom, Severity, and Day Post Dosing – 2.5 mcg ZPIV – Post Dose 1

Severity	Pre-Dose		30 mins Post-Dose		Day 1		Day 2		Day 3		Day 4		Day 5		Day 6		Day 7		Day 8+		Any Post-Dose*	
	n	%	n	%	n	%	n	%	n	%	n	%	n	%	n	%	n	%	n	%	n	%
Myalgia																						
Arthralgia																						
Headache																						
Nausea																						
Vomiting																						
Diarrhea																						
Abdominal Pain																						
Rash																						
Fever																						
In this table, subjects who reported not having a symptom are listed as “None”.																						
Subjects who were not seen for assessment nor completed a memory aid, or subjects who could not remember whether they had a symptom are listed as “Not Reported”.																						
N = Number of subjects in the Safety population and dosage group who received the specified dose.																						
n = Number of subjects reporting an event																						
Severity is the maximum severity reported post dosing for each subject for each day.																						
* Maximum severity post dosing for each subject over all days.																						

Tables with similar format:

2.5 mcg ZPIV

Table 67: Number and Percentage of Subjects Experiencing Solicited Local Events by Symptom, Severity, and Day Post Dosing – 2.5 mcg ZPIV – Post Dose 2

[Implementation note: N = Number of subjects in the Safety population and dosage group who received the specified dose.]

Table 68: Number and Percentage of Subjects Experiencing Solicited Local Events by Symptom, Severity, and Day Post Dosing – 2.5 mcg ZPIV – Post Any Dose

[Implementation note: N = Number of subjects in the Safety population and dosage group]

5 mcg ZPIV

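### Table 45 divides solicited-event rates by everyone dosed, so subjects with no usable solicited data count as event-free; the size is probably small, and the N in Tables 46–51 also needs correcting

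*SAP*

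**What the plan says.** Primary endpoint 1 (SAP 3.2) is the frequency and severity of solicited reactions through Day 8 after each dose. Tables 45–51 carry the per-symptom percentages and exact intervals that protocol 11.4.2 asks for.

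- **Table 45.** The note reads "N = Number of subjects in the safety population who received the specified dose; used as the denominator for percentages", and the numerator is "n = Number of subjects reporting an event". The shell has no Not Reported row.
- **SAP 9.3**, for adverse event incidence generally: "the denominator will be the total treatment group size or the corresponding number of subjects receiving the second dose, as appropriate".
- **Tables 46–51** (strata by baseline serostatus): "N = Number of subjects in the Safety population with the specified flavivirus immune status at baseline". Receipt of the dose is not mentioned.
- **Tables 44, 52 and 59.** None and Not Reported are separate categories; "subjects who did not complete their Memory Aid or could not remember whether they had a symptom are listed as" Not Reported.
- **Table 66**, by day, defines the category differently. "Subjects who were not seen for assessment nor completed a memory aid" fall into it, as do subjects who cannot recall the symptom.
- **SAP 9.3.1** says the data behind Tables 45–51 are "collected in-clinic pre-vaccination, post-vaccination and via memory aid".
- **SAP 6.5:** "No imputation will be performed for missing values". It also assumes that data are missing completely at random. Protocol 11.4.5 expects little missing data and gives no figure.

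**The concern.** One subject can be Not Reported in Table 52 and a non-event in Table 45. Table 45 is the display with the interval, and that interval treats the subject as fully observed. The error runs one way: whenever solicited data are missing, the rate falls below the rate among subjects actually assessed. In a Phase 1 trial whose primary purpose is tolerability, a default that can only make the vaccine look better tolerated is the wrong default.

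The rule also departs from the SAP's practice elsewhere. Immunogenicity percentages use subjects with non-missing data at the time point (SAP 8.2.1 and 8.2.2). The tables of treatment-related laboratory abnormalities require an available result (Table 201 note), and the vital-sign tables require available data (Table 232 note). Table 195 prints a Missing column.

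Table 43, which compares the dosage groups, counts post-dose events against the same dosed Ns. If missingness differed between arms, those comparisons would shift too.

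**Working it through.** **The plan's own figure.** The documents state no solicited-event rate and no expected share of Not Reported. The related figure in SAP section 5 is the chance of seeing at least one event in 35 subjects at a true rate of 4.5%: 1 − (1 − 0.045)^35 = 80.0%, as stated. It presumes that all 35 are observed. With 33 assessed it is 78.1%, and with 31 it is 76.0%.

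**Inputs.** SAP 4.4.3 gives 45 recipients of 5 mcg, 35 of 2.5 mcg and 5 placebo in each group. SAP 6.1 uses a single placebo column, so 5 + 5 = 10. The number m with no usable solicited data, and the event rate r among those assessed, are assumptions.

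**Formula.** For x subjects with an event, the planned rate is x/N and the observed-data rate is x/(N − m). Their ratio is (N − m)/N, and the understatement in percentage points is 100 × r × m/N. If data are missing completely at random, x/(N − m) is unbiased and x/N is low by that factor.

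| Column | N | m | (N − m)/N | Points lost at r = 40% |
|---|---|---|---|---|
| 2.5 mcg | 35 | 1 | 0.971 | 1.1 |
| 2.5 mcg | 35 | 2 | 0.943 | 2.3 |
| 2.5 mcg | 35 | 4 | 0.886 | 4.6 |
| 5 mcg | 45 | 1 | 0.978 | 0.9 |
| 5 mcg | 45 | 2 | 0.956 | 1.8 |
| 5 mcg | 45 | 4 | 0.911 | 3.6 |
| Placebo | 10 | 1 | 0.900 | 4.0 |
| Placebo | 10 | 2 | 0.800 | 8.0 |

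Over r = 20% to 60%, the loss is 0.6 to 6.9 points for N = 35 with m = 1 to 4, 0.4 to 5.3 for N = 45 with m = 1 to 4, and 2.0 to 12.0 for N = 10 with m = 1 or 2. With m = 0 it is zero.

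**In counts**, with Clopper-Pearson 95% intervals. Here x is held fixed, so the gaps differ slightly from those above. The last column counts the missing subjects as events, (x + m)/N.

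| x, N, m | As planned | Observed data | Upper bound |
|---|---|---|---|
| 14, 35, 1 | 40.0% (23.9–57.9) | 14/34 = 41.2% (24.6–59.3) | 15/35 = 42.9% |
| 14, 35, 2 | 40.0% (23.9–57.9) | 14/33 = 42.4% (25.5–60.8) | 16/35 = 45.7% |
| 18, 45, 2 | 40.0% (25.7–55.7) | 18/43 = 41.9% (27.0–57.9) | 20/45 = 44.4% |
| 4, 10, 1 | 40.0% (12.2–73.8) | 4/9 = 44.4% (13.7–78.8) | 5/10 = 50.0% |

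**Tables 46–51.** Read literally, the post-dose-2 denominator is the whole serostatus stratum. If d of its S subjects never received dose 2, the rate is multiplied by (S − d)/S for that reason alone. The documents give no d. The single-dose notes under Tables 75 onward do keep the receipt condition, so the omission looks like an oversight.

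**The case against.** The best case for the plan has five parts.

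1. **Events do not depend on the diary.** A reader might infer that a missing memory aid by itself makes a subject event-free. It does not: clinic-collected events count. Every vaccinee is observed for at least 30 minutes with a reactogenicity assessment, followed by clinic reviews on Days 2 and 8 and a Day 4 call. This stands, and it narrows m to subjects for whom these sources together give no usable data. It also means that a denominator of subjects with any post-dose assessment would include nearly everyone, so a useful rule must look beyond the 30-minute check.
2. **Nothing is formally imputed.** A reader might call this a contradiction of SAP 6.5. It is not one in the text. SAP 9.3 declares the denominator openly, and SAP 6.1 lets each analysis define its own. What remains is an inconsistency in effect: the arithmetic is that of setting missing to no event, while the stated assumption points to the observed-data denominator.
3. **The missing counts appear elsewhere.** Tables 52–65 show Not Reported for the same symptoms, doses and arms. A reader could rebuild the rates from them, but would have to recalculate the intervals.
4. **Missing data should be few.** The protocol says so, and each observed-data rate above lies inside the planned interval. This limits the size and leaves the direction unchanged.
5. **The notes to Tables 46–51 may be shorthand.** They could be meant to add the serostatus restriction to the Table 45 note, and SAP 9.3 refers to dose-2 recipients where appropriate. That is plausible, but a programmer should not have to guess.

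**Conclusion.** The point holds as a conditional, one-directional bias in Table 45, by a factor of (N − m)/N. At an assumed 40% rate it is about 1 to 2 points for one or two missing in an active arm and about 4 points for one missing among the 10 placebo recipients. It disappears if every dosed subject has usable solicited data. Both m and the event rate are assumptions, so the documents do not show that any rate will in fact be understated.

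A reader might also infer that Hurricane Maria cost Group 1 its diaries and so makes 5 mcg look better tolerated. The documents do not support that. Protocol sections 4 and 11.2 report lost samples, say nothing of lost reactogenicity data, and keep the 11 affected subjects in the safety population.

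The missing receipt condition in Tables 46–51 is a separate wording fault, and its size depends on how many subjects did not receive dose 2.

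**What to change.** In SAP 9.3 and the notes to Tables 43 (solicited rows) and 45–51:

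- Define the denominator as subjects who received the specified dose and have solicited data for that symptom, or symptom group, after clinic discharge. The source may be the memory aid or a later clinic or phone review. The 30-minute check alone should not qualify.
- State receipt of the dose explicitly in Tables 46–51.
- Use one definition of Not Reported in Tables 44, 52, 59 and 66 and the tables that follow their formats.
- Print the Not Reported count in Tables 45–51.
- Keep the all-dosed rate as a sensitivity display, with a bound that counts Not Reported as events.

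The cost is one sentence in SAP 9.3, revised notes and a little extra table programming. No new data are needed. Where data are missing, the reported rates will be slightly less favourable.
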